4.1.2. Handling of Dropouts or Missing Data

With the exception of dates, missing data will not be imputed. The method of imputation for any dates that are imputed is described in the relevant section.

4.2. Participant Dispositions

A detailed description of patient disposition will be provided. It will include a summary of the number and percentage of patients entered into the study, rescreened after screen failure, randomized in the study, and treated in the study, reasons for discontinuation from study treatment (safety population only), and reasons for discontinuation from study (ITT population only). Reason for discontinuation from both study treatment and the study will be summarized by predetermined categories.

4.3. Primary Endpoint Analysis

4.3.1. Definition of Endpoint

The primary endpoint is investigator-assessed PFS in the ITT population. Progression-free survival is defined as the time from randomization until the first occurrence of documented disease progression per RECIST version 1.1 criteria (Eisenhauer et al. 2009), or death from any cause in the absence of progressive disease. Participants known to be alive and without disease progression will be censored according to the censoring scheme detailed in Section 4.3.2.

The final analysis of PFS will be conducted after approximately 251 investigator-assessed events have been observed in the ITT population. One interim analysis is planned for the primary endpoint of PFS, after approximately 176 events have been observed. See further details in Section 4.9.

4.3.2. Main analytical approach

The Kaplan-Meier method (Kaplan and Meier 1958) will be used to estimate the PFS curves. Median PFS and PFS rates at various time points with 95% CIs will be estimated for each arm. The comparison of PFS curves between treatment arms will be conducted by a stratified log-rank test as the primary analysis, stratified by the randomization strata. The treatment effect will be estimated by hazard ratio with its corresponding 95% CIs using the stratified Cox proportional hazard model (Cox 1972) with treatment as the only covariate, stratified by the randomization strata. A detailed PFS event/censoring scheme is provided in Table 2 below.

Table 2 PFS Censoring Scheme

| Situation | Event/Censor | Date of Event or Censor |
|--|---------------------|---|
| Tumor progression or death | Event | Earliest date of PD or death |
| No tumor progression and no death | Censored | Date of last adequate tumor assessment, per RECIST 1.1 criteria, or date of randomization (whichever is later) |
| | Unless | |
| No baseline radiologic tumor assessment available | Censored | Date of randomization |
| No adequate postbaseline tumor assessment | | |
| available and death reported after 2-scan intervals | Censored | Date of randomization |
| following randomization | | |
| New systemic anticancer therapy prior to tumor progression or death | Censored | Date of last adequate tumor assessment, per RECIST 1.1 criteria, prior to start of new therapy or date of randomization (whichever is later) |
| Tumor progression or death documented | | Date of last adequate tumor assessment |
| immediately after 2 or more missing scan intervals | Consorad | prior to 2 or more missing scans, per |
| following last adequate tumor assessment or | Celisoreu | RECIST 1.1 criteria, or date of |
| randomization (whichever is later) | | randomization (whichever is later) |

Abbreviations: CR = complete response; PD = progressive disease; RECIST 1.1 = Response Evaluation Criteria in Solid Tumors, version 1.1; SD = stable disease.

Note: Symptomatic deterioration (ie, symptomatic progression that is not radiologically confirmed per RECIST 1.1 criteria) will not be considered as tumor progression.

Note: Adequate tumor assessment per RECIST 1.1 criteria refers to an assessment with 1 of the following responses: CR, PR, SD, or PD.

Note: The 2-scan interval is counted from the date of last adequate tumor assessment to the date of next 2 scheduled tumor assessments plus 8 days (adjusted by tumor assessment window).

Note: If there are multiple dates associated with 1 assessment, the assessment date will be set to the first date when the overall response is PD and the last date otherwise.

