9.3.2. Primary Endpoint/Estimand Analysis

The primary endpoint, PFS by investigator assessment, is defined as the time from randomization until the first occurrence of documented disease progression as determined by investigator assessment per RECIST 1.1, or death from any cause in the absence of documented progressive disease. Participants known to be alive and without disease progression will be censored at the time of the last adequate tumor assessment (a detailed PFS event/censoring scheme will be provided in the SAP). PFS will be compared between treatment arms using a stratified log-rank test, stratified by the randomization strata in the ITT population. The corresponding hazard ratio between treatment arms will be estimated using a stratified Cox regression model (Cox 1972), stratified by randomization strata. PFS curves, median PFS, and PFS rates at various time points with 95% CI for each treatment arm will be estimated using the Kaplan-Meier method (Kaplan and Meier 1958). Sensitivity analyses for PFS will be described in the SAP.

CCI

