4.3.3. Sensitivity Analyses

Sensitivity analyses will be undertaken for calculation of the primary endpoint in order to evaluate the robustness of the analysis. The following sensitivity analyses will be performed for PFS:

- Using different rules for censoring (details provided in Table 3 below)
- Using an unstratified log-rank test and unstratified Cox model
- Using stratification factors based on the eCRF data if available
- Using a multivariate Cox regression model constructed by selecting variables among all the potential variables such as the variables used in the subgroup analyses, using stepwise selection method, with an entry p-value of 0.05 and an exit p-value of 0.1. The treatment factor will be kept out of the model throughout the covariate selection process and only added to the final model

CONFIDENTIAL

| Definition | Situation | Event/ Censor | Date of Event or Censor |
|---|--|------------------|---------------------------------|
| SA1: Ignoring absence of adequate postbaseline tumor assessment | No adequate postbaseline tumor assessment available and death reported after 2-scan intervals following randomization | Event | Death |
| SA2: Ignoring missing tumor assessments | PD or death documented after 2 or more missing scan intervals following last adequate tumor assessment or randomization (whichever is later) | Event | Earliest date of PD or death |
| SA3: Symptomatic progression as a PFS event | Symptomatic progression that is not radiologically confirmed per RECIST 1.1 criteria | Event | Date of symptomatic progression |

Table 3 PFS Censoring Scheme for Sensitivity Analyses

Abbreviations: PD = progressive disease; PFS = progression-free survival; RECIST 1.1 = Response Evaluation Criteria in Solid Tumors, version 1.1.; SA = sensitivity analysis.

Other sensitivity analyses for PFS may be conducted if deemed appropriate.

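### SAP Table 2 censors a participant with no baseline scan at randomization even after an early death, which SAP 4.3.1 and the adjacent row would count as a PFS event

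*SAP*

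**What the plan says.** SAP 4.3.1 makes investigator-assessed PFS in the ITT population the primary endpoint. The event is documented progression "or death from any cause in the absence of progressive disease". On censoring, the same section says: "Participants known to be alive and without disease progression will be censored according to the censoring scheme". Protocol 9.3.2 also counts "death from any cause in the absence of documented progressive disease" and leaves the detailed event and censoring scheme to the SAP.

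SAP Table 2 (section 4.3.2) starts from the general rule "Tumor progression or death | Event | Earliest date of PD or death". Four exceptions follow under the word *Unless*. The first, "No baseline radiologic tumor assessment available", is censored at the date of randomization and says nothing about death. The second censors at randomization a participant with no adequate post-baseline assessment, but only if death is reported after 2 scan intervals. The third covers new anticancer therapy, and the fourth covers two or more missing scan intervals.

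SAP Table 3 (section 4.3.3) has three alternative censoring schemes. SA1 turns the second exception into an event; its situation is "No adequate postbaseline tumor assessment available and death reported after 2-scan intervals following randomization". SA2 does the same for the missing-scan exception. SA3 adds symptomatic progression. None of them names the no-baseline exception. The other listed sensitivity analyses change the strata or covariates, not the censoring, and further ones are optional.

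**The concern.** A baseline scan is needed to judge RECIST progression. It is not needed to establish that someone has died. Read literally, the no-baseline exception gives an ITT participant with a known early death no follow-up time and no event, although 4.3.1 counts that death and describes censoring only for participants alive without progression.

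The adjacent row shows that the SAP accepts an early death as an event without any post-baseline scan. The no-baseline row lacks the time limit that the adjacent row carries, so two participants who die on the same day can be handled in opposite ways. The death should be known: Protocol 8.1.2 keeps randomized but untreated participants under monitoring, and Protocol 7.3 seeks survival status for randomized participants who are lost to follow-up.

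At stake is whether the primary analysis follows its own endpoint definition for a handful of participants at most.

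**Working it through.** **The plan's own figures.** Inputs from SAP 4.9.3, Table 6 and section 5: HR 0.70, one-sided alpha 0.025, 176 interim and 251 final events, 1:1 allocation.

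- Fixed-design events (Schoenfeld): 4(1.960 + 0.842)² / (ln 0.70)² = 247. The Freedman formula gives 253. The planned 251 lies between them.
- Fixed-design power at 251 events: Φ(√(251/4) × 0.357 − 1.960) = 0.807.
- Two looks with O'Brien-Fleming-type Lan-DeMets spending at 176/251: one-sided p boundaries 0.0074 and 0.0227, critical HRs 0.69 and 0.78, cumulative power 0.472 and 0.801.

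These match Table 6. The point does not depend on them, but they give the scale for the illustration below.

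**The rules side by side.** Take a participant with no recorded progression, no new therapy and no post-baseline scan, who dies.

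| | Death within 2 scan intervals | Death later |
|---|---|---|
| Baseline scan available | Event on date of death | Censored at randomization; SA1 makes it an event |
| No baseline scan | Censored at randomization; not reached by SA1, SA2 or SA3 | Censored at randomization; fits the SA1 wording, but precedence between rows is not stated |

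Scans are about every 8 weeks in the first 12 months (Protocol 1.3), and the note to Table 2 adds 8 days. Two scan intervals counted from randomization are therefore about 2 × 56 + 8 = 120 days, ignoring any gap between randomization and Cycle 1 Day 1. The lower-left cell is the anomaly.

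**Size.** The documents give no expected count. I assume k = 0 to 2 such deaths, at most 2/251 = 0.8% of the planned events. As an illustration, take an observed HR of 0.78 at 251 events:

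- Log-rank score: U = ln(0.78) × 251/4 = −15.59, with information V = 251/4 = 62.75, so z = 15.59/√62.75 = 1.97.
- Early on, the arms have about equal numbers at risk, so each restored death adds +0.5 to U if it is in Arm A and −0.5 if it is in Arm B. V becomes (251 + k)/4.
- HR = exp(U/V), and z = −U/√V.

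| k | All in Arm A: HR (z) | All in Arm B: HR (z) |
|---|---|---|
| 0 | 0.780 (1.97) | 0.780 (1.97) |
| 1 | 0.787 (1.90) | 0.775 (2.03) |
| 2 | 0.794 (1.84) | 0.769 (2.09) |

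The final critical z is 2.00. One death moves z by about 0.06 to 0.07, which matters only for a result already at the boundary, and in either direction. Because the analysis is event-driven, restored deaths would count towards the 251. Planned events, alpha and power stay the same.

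**The case against.** **The situation should hardly arise.** Protocol 1.3 places baseline assessments in screening and requires eligibility to be confirmed before randomization. Inclusion criteria 4 and 5 require radiologic evidence of progression and measurable or evaluable disease. Protocol section 5 allows no waivers. SAP 4.1.1 accepts a first assessment made after randomization but before first dose as the baseline. All of this stands, and it is why the assumed range is short and includes zero.

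**Bias.** A reader might infer that missing baseline scans cluster in participants who deteriorate around randomization, and so distort the comparison. The documents do not support this. Baseline imaging comes before randomization in a double-blind trial, and later deterioration cannot remove a scan already taken.

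**Sensitivity analyses.** A reader might also infer that no sensitivity analysis restores any death without a baseline scan. That goes too far. Such a participant would generally have no adequate post-baseline assessment either, so a death after 2 scan intervals meets the SA1 wording. Only the early deaths are clearly out of reach.

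**Censoring some deaths is the general design.** The other three exceptions name death and still censor, and no Table 3 analysis reverses the new-therapy row. Protocol 9.3.2 delegates the scheme to the SAP. This is fair: departing from 4.3.1 is not in itself an error. But it does not explain why an early death is an event in one row and not in the row beside it.

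**The row might be meant only for participants who are alive,** since it does not mention death. The text does not say so, and if that is the intention the same added clause makes it clear.

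**Conclusion.** The point holds for deaths within 2 scan intervals of randomization in participants with no baseline radiologic assessment. Table 2 as written drops them from primary PFS, contrary to SAP 4.3.1 and out of line with the adjacent row, and no prespecified sensitivity analysis brings them back. For later deaths the SAP is unclear rather than silent, because SA1 may apply but no order between rows is given.

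The practical effect is very small. On the assumed 0 to 2 deaths, the HR in the illustration moves by at most about 0.014 (0.780 to 0.794), with no predictable direction. Nothing here shows bias between arms or a loss of power. Every such death still counts in overall survival (SAP 4.4.1.1). SAP 4.4.2 applies the investigator-PFS methods to centrally reviewed PFS, so the same row would carry over there unless the separate Central Review SAP says otherwise. This is a drafting correction worth making, not a threat to the primary result.

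**What to change.** In SAP Table 2, limit the situation to: "No baseline radiologic tumor assessment available" and no death within 2 scan intervals of randomization, censored at the date of randomization. A death inside that window is then an event on the date of death, as in the adjacent row. In Table 3, state that SA1 also counts later deaths in participants with no baseline assessment, which settles the overlap between rows.

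This does not restore every death to the primary analysis, since later ones stay censored there. It applies the SAP's existing convention for deaths without scans and leaves the later deaths to SA1. The Central Review SAP should be checked for the same wording.

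The cost is one clause in each table, with no new data and no change to planned events, alpha or power. Protocol 9.3.1 requires such clarifications to be described and justified in the SAP before unblinding.

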4.3.3. Sensitivity Analyses

Sensitivity analyses will be undertaken for calculation of the primary endpoint in order to evaluate the robustness of the analysis. The following sensitivity analyses will be performed for PFS:

- Using different rules for censoring (details provided in Table 3 below)
- Using an unstratified log-rank test and unstratified Cox model
- Using stratification factors based on the eCRF data if available
- Using a multivariate Cox regression model constructed by selecting variables among all the potential variables such as the variables used in the subgroup analyses, using stepwise selection method, with an entry p-value of 0.05 and an exit p-value of 0.1. The treatment factor will be kept out of the model throughout the covariate selection process and only added to the final model

CONFIDENTIAL

| Definition | Situation | Event/ Censor | Date of Event or Censor |
|---|--|------------------|---------------------------------|
| SA1: Ignoring absence of adequate postbaseline tumor assessment | No adequate postbaseline tumor assessment available and death reported after 2-scan intervals following randomization | Event | Death |
| SA2: Ignoring missing tumor assessments | PD or death documented after 2 or more missing scan intervals following last adequate tumor assessment or randomization (whichever is later) | Event | Earliest date of PD or death |
| SA3: Symptomatic progression as a PFS event | Symptomatic progression that is not radiologically confirmed per RECIST 1.1 criteria | Event | Date of symptomatic progression |

Table 3 PFS Censoring Scheme for Sensitivity Analyses

Abbreviations: PD = progressive disease; PFS = progression-free survival; RECIST 1.1 = Response Evaluation Criteria in Solid Tumors, version 1.1.; SA = sensitivity analysis.

Other sensitivity analyses for PFS may be conducted if deemed appropriate.

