9.3. Statistical Analyses

9.3.1. General Considerations

Participants will be randomized using the following stratification factors:

• Geography (3 levels)

- Presence of visceral metastases (2 levels)
 - o Yes, or
 - o No

CCI

• Duration on prior adjuvant/metastatic CDK4 & 6 inhibitor-based regimen (2 levels):

Any modifications or clarifications to the data analysis methods will be described and justified in the SAP before unblinding.

The primary analysis of the primary endpoint of PFS is event driven and will be performed when the required number of PFS events has been observed (for interim and final analyses). See Sections 9.4.2 and 9.5. All secondary endpoints will be evaluated at this time. Additional updated analyses of efficacy and safety may be conducted at later times if deemed appropriate by the Sponsor.

Handling of missing, unused, and spurious data is addressed prospectively in the overall statistical methods described in the SAP, where appropriate. Adjustments to the planned analyses will be described in the final CSR.

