4.8.10. Subgroup analyses

Subgroup analyses of PFS and OS will be performed for potential prognostic subgroup variables, including

- all baseline stratification factors
- measurable disease at baseline (yes versus no)
- age (<65 years versus \geq 65 years)
- race (Caucasian, Asian, and Other)
- progesterone receptor status (positive versus negative)
- baseline ECOG PS (0 versus 1)
- number of sites involved (1 versus 2 versus 3+)
- prior CDK4/6 inhibitor (abemaciclib versus palbociclib versus ribociclib), and

• prior CDK4/6 inhibitor setting (adjuvant versus locally advanced/metastatic)

If a level of a factor consists of fewer than 5% of randomized patients, analysis within that level will be omitted. Analyses will be done within subgroup and, separately, across subgroups with a test of interactions of subgroups with treatment performed. Estimated hazard ratios and CIs for the within subgroup analyses will be presented as a forest plot along with p-values for tests of interactions between subgroup variables and treatment. Other subgroup analyses may be performed as deemed appropriate. If any safety analyses identify important imbalances between arms, subgroup analyses of these endpoints may be performed.

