Abbreviations: HR = hazard ratio; PFS = progression-free survival; NA = not applicable.

5. Sample Size Determination

The study will randomize approximately 350 participants in 1:1 randomization ratio, with approximately 175 participants per treatment arm.

A 2-look group-sequential design of the primary endpoint of investigator-assessed PFS will be used to accommodate an event-driven plan for an interim PFS and final PFS analyses. The interim efficacy analysis will be performed after approximately 176 PFS events in total have occurred (ie, approximately 70% of the planned PFS events).

The final PFS analysis will be performed after approximately 251 PFS events in total have occurred (that is, an approximately 30% censoring rate). Assuming a hazard ratio of 0.70, this sample size yields approximately 80% statistical power to detect superiority for the abemaciclib plus fulvestrant arm versus the placebo plus fulvestrant arm.

This will be conducted with a one-sided log-rank test and a cumulative Type I error of 0.025.

6. Supporting Documentation

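### Does the stepwise covariate-adjusted PFS sensitivity model need a fixed, named covariate list?

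*SAP*

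**What the plan says.** SAP 4.3.3 lists four kinds of sensitivity analysis for PFS: alternative censoring rules, an unstratified analysis, stratification by eCRF values, and a multivariable Cox model. The last is "constructed by selecting variables among all the potential variables such as the variables used in the subgroup analyses". The rule for entering and removing covariates is also given: "using stepwise selection method, with an entry p-value of 0.05 and an exit p-value of 0.1". On the treatment term the bullet adds: "The treatment factor will be kept out of the model throughout the covariate selection process and only added to the final model".

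The subgroup variables it points to are itemised in SAP 4.8.10. There are 11: the three randomisation factors ("all baseline stratification factors") and eight others, namely measurable disease, age, race, progesterone receptor status, ECOG PS, number of sites, prior CDK4/6 inhibitor and prior inhibitor setting.

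Elsewhere the SAP is explicit about stratification. The main Cox model in 4.3.2 is stratified by the randomisation strata, and another bullet in 4.3.3 reads "Using an unstratified log-rank test and unstratified Cox model". The multivariable bullet says neither. Protocol 9.3.2 leaves PFS sensitivity analyses to the SAP, and Protocol 9.3.1 states: "Any modifications or clarifications to the data analysis methods will be described and justified in the SAP before unblinding".

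**The concern.** A sensitivity analysis supports the primary result best when a reader can write down its model beforehand. Here nobody can. The pool is introduced by example and so is nominally open, p-values decide what enters, and no covariate is forced in, not even those used to stratify randomisation. Two programmers could also differ on whether to stratify.

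PFS is tested more than once ("One interim analysis is planned for the primary endpoint of PFS, after approximately 176 events have been observed", then a final analysis at about 251). If this model were run both times, the adjusted hazard ratio might move because the covariates changed rather than because the data did. At stake is the weight this analysis can carry as evidence of robustness. The primary test is not at stake.

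**Working it through.** **1. The plan's own figures, and whether they depend on this model.** Inputs from SAP 4.9.3 and Section 5: 176 and 251 events, HR 0.70, O'Brien-Fleming-type spending, and "a one-sided log-rank test and a cumulative Type I error of 0.025".

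- Information fraction: t = 176/251 = 0.701.
- Interim alpha: 2[1 - Φ(2.241/√0.701)] = 0.0074, so z = 2.436. The final boundary is z = 2.000, p = 0.0227.
- HR bounds, exp(-2z/√d): exp(-2 × 2.436/√176) = 0.693 and exp(-2 × 2.000/√251) = 0.777.
- Power: 0.472 at the interim, 0.801 cumulative.

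All agree with Table 6. None uses the multivariable model, and SAP Section 2 restricts error control to PFS and OS.

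**2. How unstable is the covariate set?** If none of the 11 listed variables is prognostic and each is an independent test at 0.05, the expected number entering by chance is 11 × 0.05 = 0.55, and the chance of at least one is 1 - 0.95^11 = 43%. For a balanced binary factor with prognostic HR 1.3, the entry statistic has mean √(d × 0.25) × ln 1.3:

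- 251 events: 7.92 × 0.262 = 2.08, entry probability 55%.
- 176 events: 6.63 × 0.262 = 1.74, entry probability 41%.

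The set is therefore unstable. In 150 simulated trials (11 binary candidates, the three randomisation factors at HR 1.3 each, treatment HR 0.70), at least one randomisation factor was left out in 87%, and 44 different sets appeared.

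**3. Does that reach the treatment estimate?** In those 150 trials the mean treatment HR was 0.705 (stepwise), 0.700 (randomisation factors always in) and 0.711 (unadjusted). The SD of the stepwise-minus-fixed difference in log HR was 0.017, against a standard error of about 2/√251 = 0.126.

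A larger simulation used 2,500 trials per scenario: 350 patients, blocks within 3 × 2 × 2 = 12 strata, the 11 candidates (15 degrees of freedom), and five prognostic factors with log HR 0.2, 0.3 or 0.4. The fixed comparator held treatment, the three randomisation factors, ECOG PS, number of sites and progesterone receptor status. At 251 events, true HR 0.70, log HR 0.3:

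| Model | Mean HR | Nominal SE | Empirical SD | Coverage | Power |
|---|---|---|---|---|---|
| Stepwise | 0.702 | 0.1286 | 0.1294 | 94.8% | 78.8% |
| Fixed, factors as covariates | 0.694 | 0.1294 | 0.1309 | 95.0% | 80.7% |
| Fixed, stratified | 0.696 | 0.1334 | 0.1334 | 95.0% | 78.2% |

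At a true HR of 1, one-sided error was 1.9% for stepwise and 2.2% for the fixed model (Monte Carlo SE about 0.3 points). Across scenarios, stepwise and fixed HRs differed by 1.4-2.1% on average, and the nominal 0.025 verdict differed in 3-4% of trials. The fixed covariate model's extra 1.9 points of power come from a mean estimate slightly beyond 0.70, not from better precision: ln(0.702/0.694) = 0.0115, or 0.09 of a standard error, is worth about 0.28 × 0.09 = 2.5 points near 80% power (0.28 is the normal density at z = 0.84).

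**4. Stratified or not?** A factor is constant within the strata it defines, so a Cox model stratified by it cannot estimate its coefficient. If the randomisation factors are candidates, as the pointer to 4.8.10 implies, the model has to be unstratified. The two silences thus largely resolve each other.

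**5. Interim against final.** SAP 4.3.1 and 4.9.3 plan interim testing of PFS but do not say that this model is run at 176 events. If it were, the log HR would be expected to move between looks with SD √(4/176 - 4/251) = √(0.0227 - 0.0159) = 0.082, an average absolute move of 0.798 × 0.082 = 0.066. That is well above the 1.4-2.1% average effect of selecting rather than fixing covariates.

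**The case for a change.** The best case for acting is that the text is open where a few words would close it. In the larger simulation the selected set differed between 176 and 251 events in 70-77% of trials if unstratified and 56-63% if stratified. Stratifying or not moved the stepwise HR by 2.8-2.9% on average and changed the nominal verdict in 6-7% of trials, so the unstated choice matters more than the selection. SAP 4.1.2 rules out imputation except for dates, so the patients analysed could also vary with the selected set.

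The factual part stands: the pool is nominally open and stratification is unstated. The consequences are weaker. Changed sets are not changed conclusions. The 2.8-2.9% figure sets the natural reading beside one in which the listed randomisation factors cannot be candidates at all. The verdict counts apply a threshold to an analysis that carries no alpha. Most candidates are needed for eligibility or randomisation, so few should be missing; race and progesterone receptor status are the likeliest exceptions.

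Nor is a fixed list clearly better. Choosing ECOG PS, number of sites and progesterone receptor status over, say, prior inhibitor or setting is a preference on which statisticians would differ. A stratified fixed model has a standard error 3.6-4.0% larger than stepwise.

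**Conclusion.** No change is needed. The rule is prespecified where it matters for bias: method, thresholds, source list, and treatment kept out of selection, in an SAP whose version history places approval before planned unblinding. Not knowing the final covariate set in advance is a property of any selection rule. An analyst would naturally take the 4.8.10 list as the pool and fit the model unstratified. Recording that in the programming specification would be tidy but alters no conclusion.

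Followed as written, the plan gives a well-calibrated supportive estimate: within 1% of the true HR on average, and 1.4-2.1% from a fixed model. The stratified primary test, its boundaries and its power are untouched, and the other analyses in 4.3.3 also bear on robustness.

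The simulated sizes rest on assumed prevalences, independent covariates, exponential PFS and prognostic log HRs of 0.2-0.4, none of which the documents supply. Correlated covariates, such as visceral disease with number of sites, would change the set-change percentages. That treatment stays out of the selection and that the primary analysis is unaffected do not depend on those assumptions.
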